#### b) Innovation

A number of current researchers are exploring combined treatment for smoking cessation. Targeting the hormonal milieu to develop novel treatments for female smokers is a novel new direction. Although previous studies compared the different phases of menstrual cycle for smoking cessation outcomes, no previous study has directly modified the hormonal milieu. Second, the use of progesterone as an adjunct to NRT for smoking cessation is innovative. This study will translate findings from pre-clinical and human laboratory studies into treatment development by testing the efficacy of progesterone for smoking cessation in a clinical trial. Third, we also propose to evaluate response inhibition as the cognitive mediator of progesterone's therapeutic effects on nicotine addiction. Data on response inhibition will shed light on how, as well as if, progesterone is effective in this population. Lastly, we will assay hormone levels to provide a direct assessment of the role of gonadal steroids (estrogen and progesterone) on likelihood of smoking abstinence.

#### Previous research

As summarized above, our human laboratory and outpatient studies have demonstrated the safety and potential efficacy of micronized progesterone for smoking cessation in regularly cycling women.

We have extensive experience in recruiting and conducting clinical trials with pre-menopausal cigarette smokers. [name] is an expert in medications development and laboratory studies

for medications development; [name] is an expert in treatment of women with mental health and addiction problems (see attached biosketches). She has conducted numerous menstrual cycle studies as well as studies on women and addiction. As an example of our successful collaboration, we have completed the first study examining progesterone's safety and effectiveness in postpartum women with cocaine use disorder (2).

We have successfully recruited and retained women in prior studies. In a study of progesterone for treatment of postpartum cocaine users (R21 DA029914), we recruited the targeted 50 women and retained 82% in a 12-week clinical trial. In an ongoing study, R01 DA034243 we have recruited 423 women, including more than 250 reproductive aged women who smoke, to a randomized clinical trial of screening, motivational interviewing and referral to substance abuse treatment. Retention at 1, 3 and 6 months has been 86%, 83% and 83%, respectively.

3. **Research Plan:** Summarize the study design and research procedures using non-technical language that can be readily understood by someone outside the discipline. Be sure to distinguish between standard of care vs. research procedures when applicable, and include any flowcharts of visits specifying their individual times and lengths. Describe the setting in which the research will take place.

#### *Overview of the study design*

This will be a double-blind, placebo-controlled, pilot, randomized clinical trial. A total of 50 women who have regular menstrual cycles will be randomized to either progesterone (200 mgs BID) + Transdermal Nicotine Patch (TNP; 21 or 14 mg/day) or placebo + TNP (21 mg or 14mg/day) for 8 weeks. TNP will be tapered after 4-6 weeks as recommended by the Clinical Practice Guidelines for treating tobacco dependence (9). Participants who smoke more than 10 cigarettes per day will receive the following dose of TNP: 21mg/24 hours for 4 weeks, 14mg for weeks 5 and 6 and 7 mg for weeks 7 and 8. Participants who smoke between 5-10 cigarettes per day will receive the following dose of TNP: 14mg/24 hours for 6 weeks, 7mg for weeks 7 and 8.

Study medications will be discontinued at the end of Week 8. All participants will also be provided behavioral treatment for smoking cessation. Participants will be inducted onto progesterone (or placebo) + TNP over a one-week period (Week 1) during the mid luteal phase, within a week before menses and the target quit date will be set for the 5 (+/-2) days after onset of menses. Participants will have post-trial follow-up visits at 1 and 3 months following the end of the trial. The main study outcomes will be self-report of smoking abstinence, biochemically verified smoking abstinence, measures of cigarette craving and nicotine withdrawal, and measures of response inhibition.

#### *Human subjects*

**Recruitment:** Recruitment will take place over 1.5 years, requiring enrollment of approximately 2-3 subjects per month. In our previous studies, we have been able to recruit on average 4 female smokers per month. Recruitment is further explained in Human Subjects but will be accomplished by direct screening in our reproductive health centers (20% of women seen for services in these centers are smokers), direct mail invitations, posters and flyers placed in local obstetrician-gynecologist offices. We have successfully used these techniques to recruit substance users, smokers and women with premenstrual dysphoric disorder in prior clinical trials. [name] has a secondary appointment in Obstetrics & Gynecology and has conducted numerous studies that entailed screening women in the reproductive health settings of Yale New Haven Hospital and their faculty (see Biosketch).

Update June 2017: All participants had blood levels of progesterone drawn. We were blind to assignment of participants but at the end of the study found that those who were randomized to active progesterone had low progesterone levels. This could be due to the progesterone preparation or the fact that smokers metabolize it very quickly. In any case, the low progesterone levels in the active treatment group obviates our ability to test our hypothesis that progesterone augmentation assists abstinence for smokers. Given the lack of funds, we cannot repeat the project. Rather, we are recruiting a second cohort and are using a commercially available oral micronized progesterone rather than the previous medication that was compounded for the study. We plan to enroll a minimum of 12 people with an imbalanced ratio of 6 active to 1 placebo. We will continue to obtain plasma levels of progesterone. This will enhance our ability to test our hypothesis. If need be in a final analysis, and give that this is a pilot project, we may be able to use the participants randomized to placebo in the first cohort and second cohort and the participants randomized to active in the second cohort.

Update September 2017: We request an additional blood draw (timeline is around Visit #6 or #7 to confirm progesterone plasma levels and compliance with pill taking. The second blood draw will be the same as the first one, completed at a professional lab on the first floor of the research site building. Approximately 6 ccs of blood will be drawn for each.

Urn Randomization: To increase the likelihood that the two groups are balanced for age and the amount of smoking, participants will be assigned to the two study conditions through “urn” randomization (Stout *et al*, 1994). A categorical variable will be created based on the number of cigarettes/day in the month before randomization: 1= $<15$ ; and 2= $\geq 15$  or more cigarettes on average, per day, to distribute severity of smoking evenly over the two groups.

Update June 2017: We plan to enroll a minimum of 12 people with an imbalanced ratio of 6 active to 1 placebo.

We will post the study on the research team’s website [www.ResearchForHer.com](http://www.ResearchForHer.com), YCCI’s Help Us Discover database, and on Yale’s Department of Psychiatry Website as well as other websites. We will also include the study in some of Yale’s online newsletters.

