Main outcomes are prolonged smoking abstinence (Y/N at each point) and rates of 7-day point prevalence of abstinence(Y/N at each point). Following the recommendations of the Society for Research on Nicotine and Tobacco workgroup, the 7-day point prevalence is defined by self-reported smoking abstinence for the last 7 days, and expired carbon monoxide <10 ppm. Prolonged smoking abstinence is self-reported smoking abstinence starting with a 2-week grace period after the quit day (i.e., last 5 weeks of the treatment phase) without relapse to: the end of the trial, 1 month and 3 months post trial. Relapse is defined by a) smoked for 7 consecutive days or b) smoked at least once each week for 2 consecutive weeks, or c) missed 2 consecutive weekly appointments or 2) failed breath test at any previous outcome assessment. Additional outcomes include measures of withdrawal (MNWS and QSU-B), and response inhibition (Stroop and SST).

Data Analysis: We will follow CONSORT guidelines for the conduct and reporting of the trial. Descriptive statistics will be used to summarize the data on all randomized subjects, although, as per CONSORT, these parameters will not be included in the statistical model for primary analyses. Aim #1: To determine whether progesterone with TNP is superior to placebo and TNP we will use generalized estimating equations (GEE), an autoregressive correlation structure a binomial distribution and either identity or log link. A time-by-treatment interaction will be included in the GEE model. The 8-week period will include a continuous version for the time variable and the follow up periods will treat time as categorical. A GEE model such as this can evaluate whether there is an overall difference between the progesterone and the placebo groups and whether the rate of change in smoking abstinence is different between the two groups. For data that are missing, we will perform inverse weighting to determine if data are missing at random (25). The weight will be the inverse of the probability not dropping out. If there are concerns of informative dropout and/or informative intermittent missing data, which is typical of clinical trial data, we will use

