pattern mixture models (26) and perform sensitivity analyses. In sensitivity analyses, participants who miss visits will be coded as smoking. Exploratory analysis will include plasma estradiol and progesterone levels as covariates in order to determine if they contribute to treatment response and PANAS scores as mediators of response to progesterone or placebo. Secondary analyses (the MNWS QSU-B) will be modelled similarly. The main outcome measures for the Stroop test are throughput and interference score. For the SST, the main outcomes are stop signal reaction time (msec) and go reaction time (msec). We will use hierarchical linear models with each cognitive measure as separate longitudinal outcomes and treatment group assignment as regressors.

**Power:** The sample size of 25 per condition was selected to provide an adequate assessment of feasibility and estimate effect sizes. Nonetheless, we determined what level of power we would have based upon a significance level of  $p < 0.05$ , 2 sided test for 7-day or prolonged abstinence. If rates of abstinence are 0.2 in the TNP only group and 0.4 in the progesterone and TNP group then the power would be 88%. If the rate of abstinence in the treated group is 0.38, power is reduced to 80%. In prior studies with the Stroop and SST, we found effect sizes  $> 0.5$  of progesterone vs placebo. Our sample size would have adequate power ( $> 80\%$ ) to detect a 2-fold difference in response. Clearly, these are large differences between groups but would provide a stable effect size estimate for a larger trial if findings are suggestive of a therapeutic effect of the combination treatment.

**Timeline:** We will use the first 3 months for study set up that will include final human subjects' approval, hiring and training of staff, database set up, computerization of the interview and assessment measures. Recruitment will begin immediately afterward. We will conduct ongoing data cleaning and will prepare reports for the human subjects' board, the DSMB and NCI at regular intervals. The final analysis and study report will occur in the last 3 months of the work period.

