We will continue to obtain plasma levels of progesterone. This will enhance our ability to test our hypothesis. If need be in a final analysis, and give that this is a pilot project, we may be able to use the participants randomized to placebo in the first cohort and second cohort and the participants randomized to active in the second cohort.

2) Transdermal Nicotine Patch (TNP): TNP is currently available as an over the counter medication as an aid for smoking cessation. Consistent with the clinical guideline, participants who smoke more than 10 cigarettes per day will receive the following dose of TNP: 21mg/24 hours for 4 weeks, 14mg for weeks 5 and 6 and 7 mg for weeks 7 and 8. Participants who smoke between 5-10 cigarettes per day will receive the following dose of TNP: 14mg/24 hours for 6 weeks, 7mg for weeks 7 and 8. Neither longer term (> 8 weeks) nor a higher dose (> 21 mg/d) of nicotine patch improves efficacy over the standard treatment. Adverse effects of TNP include skin irritation, nausea, vomiting, sweating, mood and sleep disturbances. To avoid skin irritation, participants will be instructed to place a new patch on a relatively hairless location, typically between the neck and waist at the start of each day and to rotate the site of application. Smokers who experience sleep disturbances will be instructed to remove the patch before bedtime.

3. **Source:** a) Identify the source of the drug or biologic to be used.  
Banner Pharmacaps.

b) Is the drug provided free of charge to subjects?  Yes  No

If yes, by whom? The medication is provided free of charge to the subjects, but is paid for by the grant supporting this research.

4. **Storage, Preparation and Use:** Describe the method of storage, preparation, stability information, and for parenteral products, method of sterilization and method of testing sterility and pyrogenicity.

Check applicable Investigational Drug Service utilized:

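### The fallback comparison of second-cohort active women with placebo women from both cohorts has no trigger and is not labelled non-randomised or exploratory

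*Combined protocol and SAP*

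**What the plan says.** The June 2017 update (Section V, item 3, Human subjects; repeated in Section VI.A.2, Background Information) reports that first-cohort women on active drug had low progesterone levels. It says this "obviates our ability to test our hypothesis that progesterone augmentation assists abstinence for smokers". A second cohort is therefore recruited on a commercial product in place of the compounded one: "We plan to enroll a minimum of 12 people with an imbalanced ratio of 6 active to 1 placebo". The update expects this cohort to improve the ability to test the hypothesis.

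It then gives the permission at issue, under the condition "If need be in a final analysis, and give that this is a pilot project". Controls would come from both cohorts ("we may be able to use the participants randomized to placebo in the first cohort and second cohort"); active women would come from the second cohort alone. The first cohort's active women are not in that list. A September 2017 update asks for a second blood draw "to confirm progesterone plasma levels and compliance with pill taking".

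Section V, item 12 (Statistical Considerations) does not mention cohorts. Aim 1 reads "To determine whether progesterone with TNP is superior to placebo and TNP we will use generalized estimating equations (GEE", with a time-by-treatment interaction and no cohort term. The section promises CONSORT conduct and reporting, and "Descriptive statistics will be used to summarize the data on all randomized subjects". It uses the word exploratory for the hormone-level and PANAS analyses only.

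**The concern.** In the permitted contrast every active woman comes from the second cohort, and nearly every control comes from the first. Randomisation protects only the small part of it that compares active and placebo women within the second cohort. The rest compares two groups recruited at different times.

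The plan does not say when the fallback applies, what status it has, or how it relates to the Aim 1 model. Someone following the text as written could put these women into the superiority GEE and report the result as the trial's test of progesterone. The update says that the first cohort can no longer test the hypothesis, so nothing in the plan guards against that reading.

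**Working it through.** **Plan's own figures.** The plan gives no figure for this contrast. Its one power statement for abstinence (88% for 0.20 vs 0.40 with 25 per arm, two-sided 0.05) does not reproduce: a standard two-proportion calculation gives 33%. That is a separate matter, and nothing below rests on it.

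**Inputs**
- First-cohort placebo: 25. This is an assumption from the Power paragraph ("The sample size of 25 per condition was selected to provide an adequate assessment of feasibility and estimate effect sizes"); actual enrolment is not given.
- Second cohort: minimum 12 at 6:1, so 12 x 6/7 = 10.3 active and 12 x 1/7 = 1.7 placebo, taken as 10 and 2.
- Abstinence: 0.20 on placebo, and 0.40 on active for power, both from the Power paragraph.
- Drift d: second-cohort minus first-cohort abstinence with no drug effect. The documents give no value, so d is assumed.

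**Non-concurrent share.** 25/(25 + 2) = 25/27 = 0.926.

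**Bias.** Let p be first-cohort abstinence without drug and t the drug effect.
- Expected active rate: p + d + t
- Expected control rate: [25p + 2(p + d)]/27 = p + 2d/27
- Expected difference: t + (25/27)d

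So d = +0.10 adds 0.926 x 0.10 = +0.093, and d = -0.10 adds -0.093.

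**Type I error.** Exact binomial enumeration, 10 active vs 25 + 2 placebo, p = 0.20, t = 0, two-sided 0.05:

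| Assumed drift | Bias | Chi-square | Fisher |
|---|---|---|---|
| -10 points | -9 points | 2.6% | 1.0% |
| 0 | 0 | 4.3% | 2.4% |
| +10 points | +9 points | 10.6% | 8.0% |

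**Other sizes.** With 15 to 25 first-cohort placebo women, 10 to 24 second-cohort active women and 2 to 4 second-cohort placebo women, the combinations tried give a non-concurrent share of 86% to 93%. At +10 points, type I error is 8.5% to 12.6% (chi-square) or 5.2% to 8.9% (Fisher).

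**Information in the contrast.** With no drift, power at 0.40 vs 0.20 with 10 vs 27 women is 25% (chi-square) or 22% (Fisher). The approximate 95% half-width at those rates is 1.96 x sqrt(0.24/10 + 0.16/27) = 0.339, about 34 points.

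All of these are single-time-point stand-ins for the planned GEE.

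**The case against.** The strongest reply is that the plan is more open than the missing label suggests. It says why the first cohort's active arm is set aside (low levels and a changed product), and it sets aside a whole arm rather than selected women. The permission is doubly conditional and tied to pilot status, and the sample size was chosen for feasibility and effect-size estimation. The default analysis can also be inferred: the Aim 1 GEE of progesterone against placebo, with this contrast only as a fallback. All of that stands, and it keeps the point to one of labelling and reporting. It does not close the gap. Pilot describes the trial rather than this analysis, Aim 1 is still worded as superiority, and no rule says when the fallback replaces the default.

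It is also true that the harm depends on drift. With none, the test is not inflated; with downward drift it is conservative. No passage describes a change of eligibility, counselling, patch regimen or outcome definition between cohorts. A different allocation ratio does not by itself bias the contrast, and the extra blood draw is not shown to have changed abstinence.

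Three stronger readings are tempting, and the documents do not support them:
- That a cohort difference has biased the result. No drift figure is given and none is shown to have occurred.
- That the plan makes a confirmatory claim for the commercial product. No passage does; the update speaks only of a better ability to test the hypothesis.
- That the contrast was chosen after abstinence by arm was known. The update says only that progesterone levels by arm were known.

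**Conclusion.** The point holds as a gap in status and labelling that should be fixed. The plan permits a mainly between-cohort comparison as a final analysis, without a trigger and without saying that it is non-randomised or exploratory. Confidence in that is high, because it rests on the text alone.

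The size is conditional. The 93% non-concurrent share (86% to 93% over the other sizes) rests on planned or assumed enrolment. The rise in type I error to 10.6% or 8.0% rests on an assumed +10-point drift, and drift in the other direction would reduce the error. The figures show how exposed the contrast is. They do not estimate a bias that has happened.

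**What to change.** Before second-cohort outcomes are analysed:

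1. In both copies of the June 2017 update and in Statistical Considerations, state that second-cohort active vs all placebo is a non-randomised, exploratory contrast with non-concurrent controls. Report it as an estimate with a confidence interval and make no superiority claim. Add the tipping-point drift: the estimate divided by the actual non-concurrent share. For example, at planned sizes a 20-point estimate would be fully explained by a drift of 20/0.926 = 21.6 points.
2. Report each cohort's own randomised comparison, including the first cohort's active arm. The second cohort's should be descriptive, since it has about two placebo women. Stratify by cohort any analysis that combines both arms of both cohorts.

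Two things are not asked for. A cohort term inside the exploratory contrast would rest on about two concurrent placebo women. A pooled test of all randomised women is not proposed as the efficacy test: it mixes two products, and the second cohort would carry a Mantel-Haenszel weight of only (10 x 2/12)/(10 x 2/12 + 25 x 25/50) = 1.67/14.17, about 12%.

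The cost is amendment wording, with no new data. The downside is that the cross-cohort contrast can no longer serve as a superiority test. Little is lost, given power of 22% to 25% even without drift.

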### *Study Procedures*

Recruitment: Women will be recruited by word of mouth, flyer, advertisement, direct screening and online postings. Women will be contacted by telephone or seen face to face if the screening is direct. We will obtain verbal consent from the potential participant to conduct a brief, preliminary screen. Women will be asked if they smoke at least 5 cigarettes, are receiving any medical treatment for smoking cessation, use hormonal contraceptives, use illicit substances, have regular menstrual cycles. No PHI will be collected for women who are ineligible at this point, although we will keep a list of women who were screened and ineligible so that they will not be screened again. We will also keep a de-identified (not linked) list of reasons for non-participation. Women who are provisionally not eligible or interested will be provide referrals if desired. Women who are provisionally eligible will be undergo the consenting procedure and they will be offered a face to face appointment to complete screening

and baseline assessments. If they are screened face-to-face we will obtain consent at this point and set a face-to-face assessment visit.

Determination of Eligibility and Baseline Visit: This interview will occur between estimated days 18-24 of the typical menstrual cycle. This will be a 120 minute visit. It will be broken down into two parts: 1) we will determine eligibility for the randomized clinical trial (RCT) and 2) we will obtain baseline measures for those who are eligible. The first procedure will be obtaining informed consent (please see consent procedures below). In the process of consent, we will explain to the provisionally eligible participant that part of the visit will be to determine eligibility for the RCT. For determination of eligibility, women will complete the NIDA Quickscreen (10); DSM 5 psychosis screener and DSM 5 screener for major depressive disorder, panic disorder or post-traumatic stress disorder (PTSD; current). Any positive responses on these measures will trigger an evaluation, including the SCID and assessment by a study clinician (a physician for medical issues; a psychologist, physician or social worker if the issues is an exclusionary psychiatric diagnosis) that will indicate whether or not the participant is eligible; 2) a medical history will be gathered to obtain information on allergies, especially progesterone, use of medication, pregnancy planning, history of breast cancer, deep vein thrombosis, coagulation problems, liver failure, cervical intraepithelial neoplasm, allergy to nuts, etc; and 3) nicotine intake history including use of all nicotine products, number of cigarettes smoked and use of other nicotine products in the previous month, prior treatment for smoking cessation; prior intolerance or allergy to transdermal nicotine patch; 4) laboratory tests that include urine for pregnancy, cotinine and drugs of abuse and expired breath CO.

The RA will complete a checklist that indicates eligibility criteria. The checklist will be reviewed by study clinician who will confirm that this information has been gathered and that the participant meets criteria for participation. For women who continue to be eligible, the RA and/or study clinician will ask baseline measures that include: 1) a menstrual history form including module for diagnosis of premenstrual dysphoric disorder and menstrual cycle dating, the Fagerstrom Test for Nicotine Dependence (FTND) (11); the Minnesotal Nicotine Withdrawal Scale (MNWS) (12), the Questionnaire on Smoking Urges-Brief (QSU-B) (13) and the Positive and Negative Affect Schedule(14) . They will also complete the following neurocognitive tasks: 1) the Stroop, (15) 2) Go/No Go, 3) Digit Symbol Substitution Test (part of the WAIS III), 4) The Shipley Institute of Living Scale (SILS) is a paper-and-pencil, self-administered scale that consists of a 40-item vocabulary and a 20-item pattern recognition section (16).

Randomization/Visit 1: After eligibility is confirmed and the baseline assessments are completed, women will be randomized. Women will then begin smoking cessation counseling and will receive two weeks supply of their study medication, TNP + either oral micronized progesterone or placebo. They will be instructed to apply one nicotine patch /day and to take one pill twice daily after the visit. They will be instructed to set a quit date for the 5 (+/-2) days after the onset of menses, ideally around the 3-4th day when perimenstrual symptoms have abated and before estrogen peaks. We will call them at the estimated time of menses onset to confirm dates and quit date plans. We used similar strategies in smoking studies and menstrual cycle studies (6).

Treatment Phase (Visit 2 to 8): Women will be seen for follow up around days 7-11 of their menstrual cycle, shortly after their quit date. This visit will confirm that treatment with TNP + progesterone or placebo was initiated and maintained for the estimated 2 weeks since Visit 1. Medication compliance will be assessed by pill count. Support and counseling will be

provided for the quit attempt. Assessments will be repeated although the neurocognitive battery will only be done a second time at this first follow up visit. A blood draw will be completed twice throughout the study, the first around Visit #2 and the other around Visit #6 or Visit #7 at a professional lab on the first floor of the research site building. Approximately 6 ccs of blood will be drawn for each.

Other assessments will be conducted weekly for the additional weeks of the study. Assessments will include a weekly calendar of cigarettes smoked, if any, breath CO. We will collect urine for cotinine if the breath test is negative and there are concerns about compliance with TNP. If there is a possibility that a participant is pregnant (i.e. she is not menstruating or in the week following menstruation) we will also test urine for positive pregnancy. Additionally, subjects will have brief behavioral treatment sessions for smoking abstinence.

End of study (Visit 8), Termination and follow-up: At the end of the 8-week treatment period, participants will complete their weekly ratings, collect breath CO. Participants and study staff will be asked to guess their treatment condition (progesterone or placebo) and will discontinue study capsules and TNP. All participants will be encouraged to remain abstinent from smoking (9). Follow-up visits will be scheduled at 1 and 3 months after the end of the study. At follow up, assessments of smoking and the PANAS will be repeated. We will not repeat the neurocognitive measures.

Strategies to minimize attrition and enhance follow up: We will: 1) rapidly assign study treatments after application confirmation of eligibility, 2) thoroughly explain study treatments and requirements, and 3) specify uniform procedures across treatment conditions regarding study staff's handling of participants who miss or come late to sessions. Study investigators will monitor participants who drop out and explore with the staff reasons for the dropouts. We will follow the full randomized sample, regardless of their retention in treatment, by including: 1) a thorough explanation at the consent interview of the importance of follow-ups, 2) collecting at least three verified locators who are likely to have knowledge of a subject's whereabouts, 3) paying participants to cover transportation and parking for follow-up visits.

